5.5.4.10 Time to Baseline TSC-associated Seizure Frequency

Blinded Phase only:

Time to baseline TSC-associated seizure frequency is defined as the number of reported days in IVRS, from Day 1, that it takes for the cumulative number of TSC-associated seizures experienced to be greater than or equal to the number of seizures (per 28 days) experienced during the baseline period and will be calculated as:

Date criterion was achieved – Date of Day 1 – Number of unreported days in IVRS between Day 1 and date criterion was achieved + 1

Patients who complete the trial without experiencing greater than or equal to the number of seizures (per 28 days) experienced during the baseline period, or who withdraw from the trial, will be censored at the earliest of:

- Day 99.
- The date of last dose as recorded on the 'End of Treatment Study Outcome' CRF page.

The exact day used for censoring will be the day obtained from above minus the number of unreported days in IVRS between Day 1 and the day obtained from above.

Time to baseline TSC-associated seizure frequency will be summarized on a continuous scale, by treatment arm, for patients in the ITT analysis set. The lower and upper quartiles will also be presented. The Kaplan-Meier estimates for the median time to baseline TSC-associated seizure frequency will be presented along with 95% CIs for the median and p-values from log-rank tests comparing each GWP42003-P arm with placebo. A Kaplan-Meier plot will also be produced.

The above will be repeated using Day 29 instead of Day 1 as the start day for counting the cumulative number of TSC-associated seizures.

5.5.5 Subgroup Analyses

To assess the degree of effect heterogeneity, effect modifier analyses are proposed, on the ITT analysis set, for the primary efficacy endpoint and the key secondary efficacy endpoint of $\geq 50\%$ reduction in TSC-associated seizure frequency.

For the primary efficacy endpoint, the effect modifier analysis will be performed using the negative binomial regression analysis as described in Section 5.5.2. The model will be updated to include covariates for each level of the effect being tested (excluding a reference level), individually and with interactions with time, interactions with treatment arm and interactions with time and treatment. A separate model will be used for testing each effect. The treatment ratios (GWP42003-P vs. placebo), percent reduction and 95% confidence intervals will be presented for each level of the effect. In addition, the effect by time by treatment arm interaction p-value, testing the hypothesis that the effect level treatment ratios are homogeneous, will be presented.

For the key secondary efficacy endpoint of $\geq 50\%$ reduction in TSC-associated seizure frequency, patients with a $\geq 50\%$ reduction in seizure frequency will be modelled using logistic regression, including stratified age group and treatment arm as covariates. The model will also include covariates for each level of the effect being tested (excluding a reference level), individually and with interactions with treatment arm. A separate model will be used for testing each effect. The number and percent of responders, and odds ratios and 95% confidence intervals will be presented for each level of the effect. In addition, the effect by treatment arm interaction p-value, testing the hypothesis that the effect level odds ratios are homogeneous, will be presented.

The following effects will be tested:

- Age group (1-6 years, 7-11 years, 12-17 years and 18-65 years). Note: stratified age group will be removed as a covariate for this model.
- Sex (Male, Female).
- Region (US, Rest of the World).
- Clobazam use (Yes, No).
- Valproic acid use (Yes, No).
- Levetiracetam use (Yes, No).
- Vigabatrin use (Yes, No).
- Baseline average TSC-associated seizures per 28 days (\leq observed Tertile 1, $>$ observed Tertile 1 to \leq observed Tertile 2, $>$ observed Tertile 2). The observed tertile values will be rounded to the nearest whole number.
- Number of concurrent AEDs (<3 , ≥ 3).
- Number of prior AEDs (<5 , ≥ 5).
- Number of prior and concurrent AEDs (<8 , ≥ 8).

Effects of patients taking other AED types will also be tested if the overall frequency of patients taking the AED is $>25\%$.

5.6 Safety Evaluation

5.6.1 Exposure to IMP

Blinded Phase:

Patients are required to take IMP twice daily (morning and evening). The first dose will be taken in the clinic on Day 1. The date of final dose in the treatment phase will be recorded on the CRF. The date of final dose, for patients who enter the taper period, will be recorded on the CRF at the end of taper visit.

The total number of dosing days in the treatment phase will be calculated as:

$$(\text{Date of last dose in the treatment phase} - \text{Date of Day 1}) + 1$$

The date of last dose in the treatment phase will be obtained from the CRF at the end of treatment visit.

Any missed doses during treatment should be recorded on the 'IMP Missed Doses Log' CRF page. The number of days with any missed doses and the number of days where trial medication was not taken in the AM nor PM will be summarized based on data in the treatment phase (Day 1 to end of treatment visit).

In addition, the number of days in which trial medication was taken at least once (AM or PM) will be summarized and calculated as:

$$\text{Total number of dosing days} - \text{the number of days where trial medication was not taken in the AM nor PM}$$

The number of days in which trial medication was taken both AM and PM will be summarized and calculated as:

$$\text{Total number of dosing days} - \text{the number of days with any missed doses}$$

The above summaries will be presented for all patients and repeated for patients who completed the treatment phase.

In addition, the expected daily volume of IMP to be administered during the treatment phase, once a patient has titrated to target dose, will be summarized by treatment.

The expected daily volume of IMP will be calculated as:

$$2 \times [\text{Weight (kg) at Day 1} \div 8 \text{ and rounded to the nearest 0.1}]$$

for patients randomized to the 25 mg/kg/day dose level and:

$$2 \times [\text{Weight (kg) at Day 1} \div 4 \text{ and rounded to the nearest 0.1}]$$

for patients randomized to the 50 mg/kg/day dose level.

Finally, IMP compliance will be summarized by treatment and calculated as:

$$100 \times (\text{Number of days IMP taken at least once} + \text{number of days IMP taken both AM and PM}) \div (2 \times \text{day of completion or withdrawal during the treatment period})$$

Open-label Extension:

The total number of dosing days will be calculated for the OLE and presented along with a categorical summary of patients whose largest dose was 25 mg/kg/day or less and patients whose largest dose was over 25 mg/kg/day during the OLE treatment phase.

5.6.2 Adverse Events

All reported AEs will be classified by system organ class (SOC), preferred term and lower level term using Version 19.1 of MedDRA.

Summaries will be presented by treatment arm as well as SOC and preferred term.

A blinded phase treatment emergent AE (TEAE) is defined as an AE with a start date on or after the first dose of IMP during the blinded phase up to and including the date of first dose of the OLE phase (OLE Day 1). An OLE phase TEAE is defined as an AE with a start date on or after the OLE Day 1. If an AE has a partial start date and it is unclear from the partial date (or the stop date) whether the AE started prior to or post first dose of IMP then the AE will be considered treatment emergent and if it is unclear which phase the event started, it will be assigned to both phases. If the start date of the AE is the same as the date of first dose of IMP from the blinded phase and the plausible relationship to IMP is marked on the CRF as "Prior to study medication" then the AE will not be considered treatment emergent.

An AE will be considered treatment-related if the plausibility relationship to trial medication is recorded on the CRF as 'yes'. If the data on plausibility relationship to trial medication is missing then the AE will be considered treatment-related.

An AE will be considered leading to permanent discontinuation of IMP if the action taken with IMP is recorded on the CRF as 'study medication stopped' or the outcome is recorded on the CRF as 'patient died'.

An AE will be considered leading to IMP dose reduction excluding permanent discontinuation if the action taken with IMP is recorded on the CRF as 'dose reduced', 'dose reduced temporarily' or 'study medication interrupted'.

An AE will be considered leading to temporary IMP dose reduction if the action taken with IMP is recorded on the CRF as 'dose reduced temporarily'.

An AE will be considered leading to permanent IMP dose reduction excluding permanent discontinuation if the action taken with IMP is recorded on the CRF as 'dose reduced'.

An AE will be considered fatal if the outcome is recorded on the CRF as 'patient died'.

The following summaries will be generated separately for the blinded and OLE phase (counts are by patient unless specified otherwise):

- Overall summary of AEs, including number of patients reporting each of; TEAEs, treatment related TEAEs, TEAEs leading to withdrawal, treatment related TEAEs leading to withdrawal, serious TEAEs, treatment related serious TEAEs.
- Summary of TEAEs.
- Summary of TEAEs by event.
- Summary of treatment-related TEAEs.
- Summary of treatment-related TEAEs by event.
- Summary of TEAEs by maximal severity.
- Summary of TEAEs by sex.
- Summary of serious TEAEs.
- Summary of serious TEAEs by event.
- Summary of non-serious TEAEs.
- Summary of non-serious TEAEs by event.
- Summary of treatment-related serious TEAEs.
- Summary of treatment-related serious TEAEs by event.
- Summary of TEAEs leading to permanent discontinuation of IMP.

- Summary of treatment-related TEAEs leading to permanent discontinuation of IMP.
- Summary of TEAEs leading to IMP dose reduction excluding permanent discontinuation (by resolution and overall).
- Summary of treatment-related TEAEs leading to IMP dose reduction excluding permanent discontinuation (by resolution and overall).
- Summary of TEAEs leading to temporary IMP dose reduction (by resolution and overall).
- Summary of treatment-related TEAEs leading to temporary IMP dose reduction (by resolution and overall).
- Summary of TEAEs leading to permanent IMP dose reduction excluding permanent discontinuation (by resolution and overall).
- Summary of treatment-related TEAEs leading to permanent IMP dose reduction excluding permanent discontinuation (by resolution and overall).
- Summary of fatal TEAEs.
- Summary of TEAEs by time of first onset of AE.
- Summary of TEAEs by time to AE resolution.
- Summary of TEAEs reported in $\geq 2\%$ of patients (after rounding) in the GWP42003-P treatment arms and where the incidence is greater than the placebo treatment arm.
- List of patients experiencing TEAEs by SOC and preferred term.
- Summary of pre-treatment AEs (blinded phase only).

For the summary of TEAEs by maximal severity, for each patient, the worst severity recorded by preferred term, SOC and overall will be used for summary purposes. If severity is missing, the worst case (severe) will be assumed.

For summaries by resolution, AEs with an outcome of 'recovered' or 'recovered with sequelae' will be summarized as 'Resolved' and AEs with an outcome of 'continuing', 'patient died' or those with a missing outcome will be summarized as 'Not resolved'.

For the summary of TEAEs by time of first onset of AE, data will be summarized under the following categories:

- Weeks 1 to 2 (Day 1 to 14).
- Weeks 3 to 4 (Day 15 to 28).
- Weeks 5 to 8 (Day 29 to 56).
- Weeks 9 to 12 (Day 57 to 84).
- >12 weeks (> Day 84).

The time to first onset of AE will be calculated for TEAEs as:

$$\text{Start date of AE} - \text{Date of first dose of IMP} + 1$$

If patients have multiple occurrences of an AE then the AE will be counted once for the first occurrence only. Percentages will be based on the number of patients in the safety analysis set who have a visit or follow-up call within each time period above.

For the summary of TEAEs by time to AE resolution, data will be summarized under the following categories:

- 1 week (≤ 7 days).
- 2 weeks (8 to 14 days).
- 3 weeks (15 to 21 days).
- 4 weeks (22 to 28 days).
- >4 weeks (>28 days).
- Ongoing (for AEs not resolved).

The time to AE resolution will be calculated for TEAEs as:

$$\text{Stop date of AE} - \text{Start date of AE} + 1$$

If patients have multiple occurrences of an AE then the AE will be counted once for the occurrence with the longest time to AE resolution. However, if any of the AEs are not resolved then the AE will be counted once within the 'Ongoing' category.

The start and stop day of the AE relative to the first dose of IMP (as recorded on the CRF) will be calculated as per Section 5.1.2. For partial dates, if it is clear from the partial date that the start/stop day was prior to the first dose of IMP, then 'pre' will be listed, similarly if it is clear that the event was post the first dose of IMP then 'post' will be listed as the start/stop day as appropriate.

All AEs will be listed. Listings will include the start and stop day of the AE, a flag for treatment emergence, and limited demographic information about the patient (age, sex, race and weight at screening). A separate listing will be provided for pre-treatment AEs, serious AEs and events of special interest (see Appendix 1).

5.6.3 Clinical Laboratory Evaluation

5.6.3.1 Hematology and Biochemistry

Summaries will be presented by treatment arm for each laboratory parameter at each visit. Change from baseline to each post-baseline visit will also be presented.

If values for any of the parameters are below or above the limit of quantification of the assay (BLQ or ALQ), then they will be included in the summary tables at the BLQ or ALQ thresholds. However, for estimated creatinine clearance, results >60 are reported only as ' >60 '. Hence, estimated glomerular filtration rate (eGFR) will be calculated as:

For patients who are ≥ 18 years at screening, the Cockroft-Gault equation will be used:

$$\text{eGFR (mL/min)} = [(140 - \text{age}) \times \text{weight} \times k] / \text{serum creatinine}$$

where age is measured in years, weight is measured in kg, $k = 1.23$ if male, $k = 1.04$ if female and serum creatinine is measured in $\mu\text{mol/L}$. eGFR will be indexed to body surface area (BSA) using the following formula:

$$\text{eGFR (mL/min/1.73m}^2\text{)} = \text{eGFR (mL/min)} \times 1.73/\text{BSA}$$

where BSA is based on the Du Bois and Du Bois formula:

$$\text{weight } 0.425 \times \text{height } 0.725 \times 0.007184$$

where weight is measured in kg and height is measured in cm.

For patients who are <18 years at screening, the revised Schwartz estimate will be used:

$$(36.2 \times \text{height}) / \text{serum creatinine}$$

where height is measured in cm and serum creatinine is measured in $\mu\text{mol/L}$. When available, enzymatic serum creatinine will be used. Otherwise, the Jaffe serum creatinine will be used. If height or weight is missing at the collection date, then the closest value to the sample date will be used. If there is more than one height or weight value on the same day or 2 height or weight values equally distant from the collection date, then the mean will be used. The eGFR will be summarized separately for each method.

Where laboratory samples are repeated, the baseline value is defined as the final recorded value prior to the first dose of IMP.

Shift tables for hematology and biochemistry parameters will be constructed, based upon normal ranges and GW toxicity limits (See Section 8), to determine the categorical shifts from baseline to each post-baseline visit. Values will be categorized as 'Normal', 'Low' or 'High' based on normal ranges and 'Toxicologically Low', 'Toxicologically Normal' or 'Toxicologically High' based on GW toxicity limits.

For eGFR, results will be assigned to the following grades:

- Normal: $>60 \text{ ml/min}/1.73 \text{ m}^2$
- Grade 1: $60 \text{ ml/min}/1.73 \text{ m}^2$
- Grade 2: $\geq 30 \text{ and } < 60 \text{ ml/min}/1.73 \text{ m}^2$
- Grade 3: $\geq 15 \text{ and } < 30 \text{ ml/min}/1.73 \text{ m}^2$
- Grade 4: $< 15 \text{ ml/min}/1.73 \text{ m}^2$

A separate shift table will be produced for eGFR based upon the above grades to determine the categorical shifts from baseline to each post-baseline visit.

For the blinded phase, scatter plots will be produced for each laboratory parameter presenting the maximum post baseline result divided by the upper limit of normal (ULN) on the Y-axis, and the baseline result divided by the ULN on the X-axis. However, for prothrombin international normalized ratio (INR), both axes will present the raw results rather than dividing by ULN.

An additional table will be produced for the blinded phase only, summarizing the number of patients meeting the following criteria:

- Alanine aminotransferase (ALT) $> 1 \times \text{ULN}$ at baseline
- Aspartate aminotransferase (AST) $> 1 \times \text{ULN}$ at baseline
- AT $> 1 \times \text{ULN}$ at baseline
- Treatment emergent ALT $> 3 \times \text{ULN}$, $> 5 \times \text{ULN}$ and $> 8 \times \text{ULN}$
- Treatment emergent AST $> 3 \times \text{ULN}$, $> 5 \times \text{ULN}$ and $> 8 \times \text{ULN}$
- Treatment emergent AT $> 3 \times \text{ULN}$, $> 5 \times \text{ULN}$ and $> 8 \times \text{ULN}$
- Treatment emergent AT $> 3 \times \text{ULN}$ and either bilirubin $> 2 \times \text{ULN}$ or INR > 1.5

where AT is AST or ALT, and treatment emergent is defined as criteria not met at baseline but met at any time post-baseline. The above will be summarized overall and for the following subgroups:

- Sex (Male, Female).

- Valproic acid use (Yes, No).
- Clobazam use (Yes, No).
- Valproic acid use and Clobazam use (Yes/Yes, Yes/No, No/Yes, No/No).
- Patients taking 3 or more current AEDs.
- Patients taking 4 or more current AEDs.

A separate table will be produced, by treatment arm and visit, presenting the incidence of patients with urinalysis or blood results indicative of a medical condition at Visit 1 and indicative of an adverse event after Visit 1.

All laboratory data will be listed; listings will include limited demographic information about the patient (age, sex, race and weight at baseline). Abnormal laboratory values will be listed separately.

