Tumors in TSC patients can occur in any major organ yet develop primarily in the brain, eyes, heart, kidney, skin and lungs. The random location, number, size and distribution of tumors result in a great variety of clinical manifestations, yet most patients exhibit dermatological, renal and/or neurological abnormalities, which appear at distinct developmental points. Dermatological abnormalities generally first appear in infancy or early childhood and include hypomelanotic macules, which are present in more than 90% of TSC patients, and facial angiofibromas, found in approximately 75% of TSC patients. In contrast, renal abnormalities tend not to develop until late childhood/adolescence and include angiomyolipomas (found in 50–70% of TSC patients), renal cysts (found in 25–35% of TSC patients) and, very rarely, renal-cell carcinomas (found in 2–3% of TSC patients). Neurological abnormalities first appear during embryogenesis and include cerebral cortical tubers and subependymal nodules (SENs), each of which are found in 80–90% of TSC

patients, as well as subependymal giant-cell astrocytomas (SEGAs), which are presumed to derive from SENs and are found in 5–15% of TSC patients. Whereas SENs and SEGAs are usually asymptomatic, the presence of cortical tubers is widely believed to underlie the neurologic manifestations of TSC, which include epilepsy, cognitive disability and autism.

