Table 13.3.2	Shift Table for Biochemistry Laboratory Parameters – Based on Toxicity Limits	Safety Analysis Set
Table 13.3.3	Shift Table for eGFR – Based on Derived Grades	Safety Analysis Set
Table 13.4	Summary of Liver Parameter Flags	Safety Analysis Set
Table 13.5	Incidence of Laboratory Abnormalities	Safety Analysis Set
Table 13.6	Summary of Pregnancy Test and Urine THC Screen Results	Safety Analysis Set
Table 14.1.1	Summary of Vital Signs	Safety Analysis Set
Table 14.1.2	Incidence of Clinically Significant Changes from Baseline for Vital Signs	Safety Analysis Set
Table 14.1.3	Incidence of Defined Flagged Vital Signs	Safety Analysis Set
Table 14.1.4	Incidence of Vital Signs Abnormalities	Safety Analysis Set

Table Number	Title	Analysis Set
Table 14.2.1	Summary of ECG Parameters	Safety Analysis Set
Table 14.2.2	Incidence of Defined Flagged ECG Parameter Values	Safety Analysis Set
Table 14.2.3	Incidence of ECG Abnormalities	Safety Analysis Set
Table 14.3	Summary of Columbia-Suicide Severity Rating Scale by Type	Safety Analysis Set
Table 14.4	Incidence of Physical Examination Abnormalities	Safety Analysis Set
Table 14.5	Summary of Tanner Stages	Safety Analysis Set
Table 14.6	Summary of Menstruation Details	Safety Analysis Set
Table 14.7	Summary of Patients with Inpatient Hospitalizations due to Epilepsy	Safety Analysis Set
Table 14.8.1	Summary of Plasma Concentrations	Safety Analysis Set
Table 14.8.2.1	Summary of PK Parameters (Overall and by Age Group)	Safety Analysis Set
Table 14.8.2.2	Summary of PK Parameter Metabolite to Parent Ratio (Overall and by Age Group)	Safety Analysis Set
Table 14.9	Summary of Plasma Concentrations of Concomitant Antiepileptic Drugs	Safety Analysis Set
Table 14.10	Summary of Study Medication Use and Behavior Survey	Safety Analysis Set
Table 14.11.1	Summary of Supplemental Drug Accountability Form	Safety Analysis Set
Table 14.11.2	Summary of Supplemental Adverse Event Form	Safety Analysis Set
Table 14.11.3	Summary of Site Classification Form	Safety Analysis Set

Table 18 List of OLE Phase Tables

Table Number	Title	Analysis Set
OLE Table 1.1.1	Summary of Patient Disposition by Site	OLE Safety Analysis Set
OLE Table 1.1.2	Summary of Patient Disposition During by Country	OLE Safety Analysis Set
OLE Table 1.2	Summary of Overall Patient Disposition	OLE Safety Analysis Set
OLE Table 2	Summary of Important Protocol Deviations	OLE Safety Analysis Set
OLE Table 3.1	Summary of Demographic Data	OLE Safety Analysis Set

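### Grade 1 in the eGFR shift tables is the single value 60, so these tables show no shift for any decline that stays above 60

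*SAP*

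**What the plan says.** SAP section 5.6.3.1 derives eGFR because, it explains, "for estimated creatinine clearance, results >60 are reported only as" greater than 60. Patients aged 18 or over at screening get Cockcroft-Gault indexed to body surface area. Younger patients get the revised Schwartz estimate, 36.2 × height ÷ serum creatinine. No rounding rule is stated for either result.

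The same section then says "For eGFR, results will be assigned to the following grades":

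| Category | eGFR (ml/min/1.73 m²) |
|---|---|
| Normal | > 60 |
| Grade 1 | 60 |
| Grade 2 | ≥ 30 and < 60 |
| Grade 3 | ≥ 15 and < 30 |
| Grade 4 | < 15 |

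It continues: "A separate shift table will be produced for eGFR based upon the above grades". SAP Appendix 6 lists the output for both phases, as Table 13.3.3 and OLE Table 13.3.3, under the title "Shift Table for eGFR – Based on Derived Grades".

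Other renal information is also planned in section 5.6.3.1. For every laboratory parameter, by arm and visit, "Change from baseline to each post-baseline visit will also be presented". In addition, "The eGFR will be summarized separately for each method". For creatinine, as for other biochemistry parameters, "Shift tables for hematology and biochemistry parameters will be constructed, based upon normal ranges and GW toxicity limits".

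**The concern.** A shift table is there to count patients who move between categories. Here one of the five categories is a point rather than a range, and the category above it has no subdivision. A patient can lose a large share of eGFR and stay in the same cell, provided the result stays above 60.

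Renal function is a reasonable thing to watch in this population. Protocol section 3.1 reports angiomyolipomas in 50–70% and renal cysts in 25–35% of patients with tuberous sclerosis complex, and adds that "renal abnormalities tend not to develop until late childhood/adolescence", an age range the trial includes. At stake is the sensitivity of a descriptive safety table that compares two doses with placebo and then follows patients through an extension of up to one year. No hypothesis test or efficacy endpoint is involved.

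**Working it through.** **Inputs.** The grade limits and both eGFR formulas come from SAP 5.6.3.1. The creatinine toxicity limit (at least 2.6 × the upper limit of the reference range) comes from SAP Appendix 4, Table 12. The documents give no expected baseline eGFR, so every baseline below is an assumption chosen for illustration. The plan states no figure on this point to reproduce.

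**Step 1: what is left for Grade 1.** Normal takes everything above 60. Grade 2 takes everything from 30 up to, but not including, 60. The only value at or above 30 not yet assigned is 60. This does not depend on whether a symbol beside the 60 was lost when the PDF was read, because the neighbouring bands leave nothing else.

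**Step 2: can a calculated eGFR equal 60?** Take the Schwartz formula, with height recorded to 0.1 cm and creatinine in whole µmol/L (both assumed). Setting 36.2 × h ÷ Cr = 60 and writing h = k/10 gives 3.62k = 60Cr, that is 181k = 3000Cr. Since 181 and 3000 share no factor, k must be a multiple of 3000, so the smallest possible height is 300 cm. A grid of assumed heights (70.0–180.0 cm) and creatinine values (15–150 µmol/L), 1,101 × 136 = 149,736 pairs, confirms this: none gives exactly 60. If eGFR were rounded to a whole number, 1,384 pairs (0.9%) would equal 60.

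**Step 3: how large a fall shows no shift?** Percentage fall = (baseline − 60.1) ÷ baseline. With height and weight unchanged, eGFR is inversely proportional to creatinine under both formulas, so the creatinine ratio is baseline ÷ 60.1.

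| Assumed baseline | On treatment | Fall | Creatinine ratio | Tabulated as |
|---|---|---|---|---|
| 150 | 60.1 | 89.9/150 = 59.9% | 2.50 | Normal to Normal |
| 120 | 60.1 | 59.9/120 = 49.9% | 2.00 | Normal to Normal |
| 100 | 60.1 | 39.9/100 = 39.9% | 1.66 | Normal to Normal |
| 90 | 60.1 | 29.9/90 = 33.2% | 1.50 | Normal to Normal |
| 75 | 60.1 | 14.9/75 = 19.9% | 1.25 | Normal to Normal |

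**Step 4: an adult example.** Assume a man aged 30, 70 kg, 170 cm. The Du Bois formula gives a body surface area of about 1.81 m². At creatinine 70 µmol/L, (140 − 30) × 70 × 1.23 ÷ 70 × 1.73 ÷ 1.81 gives 129.3. At 150 µmol/L the same calculation gives 60.4. That is a 53% fall, (129.3 − 60.4) ÷ 129.3, and still Normal to Normal.

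**Step 5: would the creatinine toxicity table catch it?** A patient who starts at or below the upper limit and whose creatinine doubles reaches at most 2 × that limit, short of 2.6 ×. So the toxicity-based shift table would not flag the fall from 120. The normal-range shift table might, depending on laboratory ranges the documents do not give.

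**The case against.** The strongest reply is that the plan does not rely on this table for renal safety. It reports mean and median eGFR change from baseline by arm and visit, and a consistent loss in one arm would appear there. Creatinine has a shift table on laboratory normal ranges (Table 13.2.2 and OLE Table 13.2.2), where a rise past the upper limit reads Normal to High. The blinded-phase scatter plots show the maximum post-baseline result against baseline. That is the wrong direction for eGFR but the right one for creatinine. Listings of abnormal values complete the picture. All of this stands. What it leaves open is a count per arm of patients with a substantial eGFR fall, because the continuous summaries give n, mean, standard deviation, median, minimum and maximum, and a creatinine shift depends on the reference range rather than on the size of the change.

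A reader might infer that the grades defeat the SAP's reason for deriving eGFR, since they put the cut at 60 back. The documents do not support that. The derivation is introduced in the context of how values beyond reporting limits enter the summary tables, and the continuous summaries do use the full calculated value. Only the shift tables discard it.

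A reader might also take the protocol's renal figures as evidence of a renal risk with the product. They describe structural lesions of the disease, not reduced filtration, and they say nothing about an effect of treatment.

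**Conclusion.** The point holds for the eGFR shift tables. Grade 1 is a single value that an unrounded eGFR will almost never take, and no decline that stays above 60 is visible in Table 13.3.3 or OLE Table 13.3.3. For illustration, that hides a fall of up to 49.9% from an assumed baseline of 120 and up to 33.2% from an assumed baseline of 90.

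Three limits apply:

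- A shift first appears at 60 or below, not strictly below 60, since a value of exactly 60 is Grade 1. Without rounding this makes almost no practical difference.
- That Grade 1 will be empty rests on unrounded eGFR. Under whole-number rounding it would hold a small fraction of results (0.9% of the assumed grid, which is not a forecast for the trial).
- It would be tempting to conclude that the plan cannot detect renal decline, or that a consistent loss in a dose arm would go unreported. The planned summaries, creatinine tables, plots and listings contradict that. The defect is reduced sensitivity in one pair of descriptive tables.

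It is still worth correcting, because a stated rule produces a category with almost nothing in it and the remedy needs no new data.

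**What to change.** In SAP 5.6.3.1, redefine Grade 1 as an interval with lower bound 60 and upper bound a lower limit of normal, with Normal above it. The sponsor should specify that limit and make it age-appropriate, since patients are aged 1 to 65 and two formulas are used. The documents contain no such limit, so none is proposed here. State whether eGFR is rounded before grading and, if so, to what precision.

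Add to Table 13.3.3 and OLE Table 13.3.3 the number of patients per arm with a fall from baseline of at least 25% and of at least 50%, using the eGFR already derived. These two thresholds are suggestions, not values from the documents. The SAP already counts patients by percentage change for weight (Appendix 2, Table 9), so the format is not new.

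The cost is one SAP edit and a format change in two tables. The downside is that more patients will be in Grade 1 at baseline, which the shift layout shows openly.
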